## 11.0 ADVERSE EVENTS

Adverse events (AEs) may occur during the treatment phase or during the follow-up phase. Adverse events occurring after the baseline assessment but before the treatment procedure will be documented in the subject's medical record but will not count as related to the investigational device or procedure.

Each adverse event will be recorded in the corresponding subject's CRF. Each adverse event will be judged by the Investigator as to its relationship and level of relatedness to the investigational device and/or investigational procedure. In addition, the Investigator will identify the date of onset, severity and duration of the AE. All adverse events will be monitored until they are adequately resolved or explained. If a subject reaches the 26-week follow-up visit and is experiencing a new or ongoing adverse event, the study sponsor should be contacted to discuss the need and/or methods for continued surveillance of the event.

The Investigator must submit to the Sponsor a report of any Serious Adverse Event (SAE), Serious Adverse Device Effect (SADE) or Unanticipated Adverse Device Effect (UADE) within 24 hours of knowledge of the event.

Sponsor Contact: [name]  
[contact]  
[contact]  
Email: [contact]

In addition, the Investigator will report adverse events to the reviewing IRB / EC (*as applicable*) according to the local reporting requirements.

## 12.0 RISK – BENEFIT ASSESSMENT

### 12.1 Potential Risks

Potential risks associated with the use of the Vivaer™ System do not differ from those of the commonly used devices and procedures to treat nasal obstruction and snoring discussed previously, but due to the non-surgical nature of the therapy, small treatment area, low-power delivery and lack of need for general anesthesia, the overall risk to the patient may be less than from other procedures such as RF turbinoplasty, septoplasty and/or functional rhinoplasty.

Potential risks associated with the use of the Vivaer System and/or the associated local anesthetics are outlined below. Subjects will be monitored closely as part of this study to allow for detection of symptoms, should they be present. This, in turn, should allow for early treatment or intervention, if necessary.

While there were no reports of these events in the previous feasibility study of this system, the following are adverse events or side effects that may occur as a result of the treatment:

- Infection
- Bleeding (other than intra-treatment at treatment sites and greater than anticipated by the investigator)
- Mucosal changes
- Scar formation leading to nasal obstruction
- Sensory changes at treatment site

Table 2 provides a list of anticipated observations that are expected in and around the treatment area. For reference, the incidence (reported as percentage of treated nostrils) observed in the previous feasibility study is also provided. These observations will be assessed and recorded at study visits if they occur but, being anticipated as a result of the procedure, will not be considered adverse events unless they require mitigation by the treating physician or are greater in severity, duration or degree of incidence than anticipated. If one of these types of observations is deemed to be an adverse event, it should be recorded on the study Adverse Event CRF.

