Additional Evaluations:	
Subject-reported NOSE score at 4-week and 12-week follow-up visits.
 
Subject-reported pain related to the study procedure by Visual Analog Scale immediately post-procedure and at 4-week and 12-week follow-up visits.
 
Patient Satisfaction with the study procedure 26 weeks post procedure.

Study Size:	50 subjects
Study Size Determination:	Prior study data were used to estimate the expected mean change (28.5) and standard deviation (30.3) for the change in NOSE score from baseline to 26 weeks. N=45 subjects would provide 90% power to test the study hypothesis at the one-sided alpha level of 0.05. To allow for up to 10% attrition, a total of 50 subjects will be enrolled.
Number of Sites:	Up to 10 study sites
Anticipated Study Duration:	Enrollment completion – Q4 2016; Follow-Up completion – Q3 2017
Study Visits:	Screening/Baseline, Study Procedure, 4 weeks, 12 weeks, 26 weeks

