#### Immediate Post-Procedure Care (prior to leaving the clinic)

Subjects will be asked to mark a vertical line on a 10 cm VAS scale to represent the pain level experienced on the Left Side and a separate VAS for pain experienced on the Right Side during the study procedure session. The score will include the overall pain experience from anesthesia delivery to procedure completion.

At the discretion of the physician, the following care may be provided:

- Apply compression to the treatment area with or without topical anesthetic, internally for 5 minutes.
- Apply petroleum jelly to the treatment area as needed.
- The patient should be instructed not to manipulate the treatment site for 24 hours with the exception of any necessary hemostasis.

Study subjects will be reminded of their next follow-up visit and will be scheduled within the study window.

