**8.4 Phase 4: Follow-Up and Study Exit**

The follow-up period will begin after the study procedure session. Subjects will undergo follow-up visits at **4 weeks, 12 weeks, and 26 weeks** calculated from the study procedure date. Requirements for each follow-up visit are provided in Table 1. Subjects that meet the study requirements as planned will be exited from the study at the 26-week follow up visit.

If a subject reaches the 26-week follow-up visit and is experiencing a new or ongoing adverse event, the study sponsor should be contacted to discuss the need and/or methods for continued surveillance of the event.

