**Table 1. Schedule of Assessments**

Assessments	Screening / Baseline	Study Procedure (within 30 days of Baseline visit)	Immediately Post-Treatment	4-Week Follow-Up (+/- 7 days)	12-Week Follow-Up (+/- 10 days)	26 Weeks Follow-Up (+/- 14 days)
Demographics and Medical History	X					
Physical Exam and Vital Signs	X					
Medication Review	X	X		X	X	X
Study Procedure		X				
Endoscopic Assessment of treatment area (with representative still photographs)	X	X	X	X	X	X
NOSE Score	X			X	X	X
Subjective Pain VAS			X	X	X	
Subject Satisfaction Questionnaire						X
Adverse Event review			X	X	X	X
Pregnancy test (if female)		X				

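### After the procedure day, the first scheduled adverse event review or pain rating is at day 21–35, so the schedule gives little support to Section 12.1's aim of early treatment

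*Combined protocol and SAP*

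**What the plan says.** Section 12.1 introduces the list of possible treatment effects with a statement about monitoring: "Subjects will be monitored closely as part of this study to allow for detection of symptoms, should they be present". The purpose follows: "This, in turn, should allow for early treatment or intervention, if necessary". The list includes infection and bleeding. The same section says that none of the listed events was reported in the earlier feasibility study.

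Table 1 marks AE review immediately after treatment and at three visits, headed "4-Week Follow-Up (+/- 7 days", "12-Week Follow-Up (+/- 10 days" and "26 Weeks Follow-Up (+/- 14 days". Pain is scheduled as the synopsis describes: "Subject-reported pain related to the study procedure by Visual Analog Scale immediately post-procedure and at 4-week and 12-week follow-up visits". Endoscopy likewise has no time point between immediately after treatment and week 4. Section 8.4 says: "The follow-up period will begin after the study procedure session". It names the same three visits and no earlier contact.

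The procedure-day pain score is limited to the session: "The score will include the overall pain experience from anesthesia delivery to procedure completion".

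Other relevant provisions:
- Section 10 allows safety follow-up by phone or email, but only for subjects lost to follow-up or withdrawn on the physician's judgement.
- Section 11 asks for onset date, severity and duration of each AE. It requires serious AEs, serious adverse device effects and unanticipated adverse device effects to reach the sponsor within 24 hours of being known.
- Section 8.5 has medication changes requested at each follow-up visit.
- Section 13.7 reports AEs in three intervals, the first running from the procedure to week 4.

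**The concern.** The period straight after a radiofrequency procedure is when early action on a procedure-related event would be most useful, and it has no scheduled contact. A subject with a non-serious problem in the first weeks is seen early only if he or she calls.

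A second, smaller issue is the quality of the record. The week-4 AE review does look back over the time since discharge. For an event that began and resolved before then, however, the onset, severity and duration that Section 11 requires rest on memory, unless the event left a trace in a medical record or the medication log. Pain after discharge is likewise first rated at week 4, because the procedure-day score stops at the end of the session.

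At stake are the AE counts in the first interval of Section 13.7 and how soon a subject who does not call is treated. Safety is a descriptive secondary endpoint, so the success criteria on the NOSE score are not involved.

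**Working it through.** **Inputs.** Visit weeks and windows come from Table 1. Procedure-day and 30-day percentages come from Table 2. The 50 subjects and up to 10 sites come from the synopsis. The day 7 ± 2 contact is the proposal made here.

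**Visit windows, in days from the procedure, assuming visits fall inside their windows.**
- Week 4: 4 × 7 = 28; 28 ± 7 gives day 21–35.
- Week 12: 12 × 7 = 84; 84 ± 10 gives day 74–94.
- Week 26: 26 × 7 = 182; 182 ± 14 gives day 168–196.

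**Gaps between consecutive AE reviews (shortest to longest).**
- Procedure day to week 4: 21 to 35 days.
- Week 4 to week 12: 74 − 35 = 39 to 94 − 21 = 73 days.
- Week 12 to week 26: 168 − 94 = 74 to 196 − 74 = 122 days.

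The first gap is the shortest of the three. It matters because of its position directly after treatment, not its length.

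**Effect of a contact at day 7 ± 2 (day 5–9).**
- First review earlier by 21 − 9 = 12 to 35 − 5 = 30 days.
- Remaining stretch to week 4: the same subtraction, 12 to 30 days.
- Workload if all 50 subjects are treated: about 50 contacts, on average 50/10 = 5 per site if all 10 sites are used.

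**Do existing provisions cover the interval?**
- The 24-hour rule covers serious and unanticipated events only, and runs from the moment the event is known.
- The remote contact in Section 10 covers two withdrawal categories only.
- Medication updates are first requested after the procedure at week 4.
- Pain during the session, changes still visible at the week-4 endoscopy, and events that led to physician contact or a new medication are captured without any change.

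**What Table 2 adds.** Crusting was seen in 1.7% of nostrils after the procedure and in 10.7 + 1.8 = 12.5% at 30 days. Some observations therefore appear after the procedure-day record. The table has no time point between these two, so it does not describe the interval.

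**The case against.** The strongest reply is that Section 12.1 is not contradicted. It commits to no contact frequency, and it sits beside endoscopy and AE review on the procedure day and at week 4, medication logs, follow-up of AEs until resolved or explained (Section 11) and the sponsor's watch for safety trends (Section 12.3). This stands. A reader might infer that Table 1 breaks a promise made in 12.1; the text does not support that.

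It can also be said that the events at risk of being missed, those that are non-serious and resolve untreated before week 4, need early treatment least. This is largely right for the counts. It leaves the symptomatic subject who would benefit from attention but does not call; how many such subjects there would be is unknown.

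A reader might also infer that infections or bleeds are likely to go unseen. The sponsor's stated experience of these is nil, although that does not prove the risk is nil, and procedure-day bleeding falls under the immediate endoscopy and AE review. Nor does Table 2 show missed events. The crusting was captured at the 30-day visit. The 21.8% entry for moderate soreness at 30 days is doubtful: on 56 nostrils, a denominator inferred from the crusting entries in that column, 12/56 = 21.4%, while 12/55 = 21.8% would need a different denominator. It is not relied on here.

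Finally, some text between the immediate post-procedure care instructions and Section 8.4 is missing from the copy read here and may hold discharge or call-back instructions. That could weaken the point about early treatment. It would not add a scheduled assessment to Table 1.

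**Conclusion.** The point holds in a limited form. After the procedure-day assessment the first scheduled AE review or pain rating falls at day 21–35. Until then, early detection of non-serious events depends on subjects reporting them, and short-lived events are dated by recall of up to 35 days. The schedule therefore gives little support to the early-treatment aim of Section 12.1 in the weeks right after treatment.

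This is a low-priority, cheap improvement. The documents do not allow any under-ascertainment to be sized, and they give no evidence that events were missed in the feasibility study. No success criterion, NOSE analysis or sample size changes. The conclusion rests on the scheduled assessments in Table 1, the synopsis and Section 8.4. It makes no claim about what subjects are told at discharge.

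**What to change.** Add one column to Table 1: a phone or email AE review of every treated subject at day 7 (± 2 days), done by existing site staff. Enter AEs on the existing AE case report form, count them in the first interval of Section 13.7, and flag them in the safety tables as first elicited at day 7.

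A classification rule is needed. Sections 8.5 and 12.1 turn an anticipated observation into an AE if it needs mitigation by the physician or exceeds what was anticipated, and Table 2 offers no day-7 benchmark for the second test. At this contact, tabulate symptoms of the Table 2 type as anticipated observations and class them as AEs only if they need mitigation by the treating physician. Otherwise judge their severity and duration against Table 2 at the week-4 visit. Endoscopic observations stay at the clinic visits.

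A 0–10 pain rating at the same contact is optional. Report it descriptively and apart from the VAS, which is a 10 cm line measured with a ruler.

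The cost is about 50 short contacts and a protocol amendment. More minor events will be recorded, and early counts will not be directly comparable with Table 2; a note in the safety tables should say so. How a subject who reports a problem is cared for remains with the clinical team.

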**Table 2. Treatment Area Observations (Feasibility Study)**

Observation	Post-Procedure (% treated nostrils)		30-Day Follow-Up (% treated nostrils)		90-Day Follow-Up (% treated nostrils)	
Inflammation / redness	Mild	55.9	Mild Moderate	10.7 1.8	Mild	3.7
Swelling, edema	Mild	64.4	Mild Moderate	16.1 3.6	Mild	3.7
Blanching	Mild Moderate	66.1 3.4	Mild	3.6	Mild	3.7
Numbness	Mild	5.1	No reports		No reports	
Bruising around orbital area	No reports		No reports		No reports	
Soreness, pain	Mild	15.3	Mild Moderate	3.6 21.8	No reports	
Bleeding at anesthetic injection site	Mild	5.3	No reports		No reports	
Bleeding at treatment site	Mild	3.4	No reports		No reports	
Nasal obstruction from tissue edema	Mild	45.8	Mild Moderate	5.4 1.8	No reports	
Disruption of mucosal flow / crusting	Mild	1.7	Mild Moderate	10.7 1.8	No reports	

## 12.2 Potential Benefit

Potential benefit, associated with the use of the Vivaer™ System, is to offer a safe, minimally invasive treatment method to improve nasal breathing. Improved nasal breathing may have a positive effect on quality of life and health.

## 12.3 Minimization of Anticipated Risks

Risks associated with the Vivaer System are minimized by design. In addition, risks will be minimized through the use of an Investigator with a high degree of experience in nasal surgical and minimally invasive procedures. The Investigator will receive sponsor-led training in proper use of the device, prior to study initiation and as warranted throughout the study. The sponsor will monitor the study for any trends that would indicate a safety issue. Aerin Medical technical and/or clinical representatives will attend all procedures to ensure the device performs as intended.

## 12.4 Potential Risks to Patient Confidentiality

In all clinical studies, confidentiality of protected health information may be breached due to study-related activities beyond those of routine clinical care. This risk will be minimized by not collecting personally identifying information on Case Report Forms (CRFs) or other study-related documentation to be provided to the study sponsor.

## 13.0 STATISTICAL ANALYSIS

### 13.1 Sample Size Determination

Prior study data was used to estimate the expected mean change (28.5) and standard deviation (30.3) for the change in NOSE score from baseline to 6 months (26 weeks). N=45 subjects would provide 90% power to test the study hypothesis at the one-sided alpha level of 0.05. To allow for up to 10% attrition, a total of 50 subjects will be enrolled.

### 13.2 Hypothesis Testing

The objective is to show that the mean improvement in NOSE score from baseline to 26 weeks exceeds 15 points. The null and alternative hypotheses are given by:

$$H_0: \mu_d \leq 15.0$$

$H_a: \mu_d > 15$ , where  $\mu_d$  represents the mean improvement in NOSE score from baseline to 26 weeks. The hypothesis is tested at the one-sided alpha 0.05 level.

### 13.3 Definition of Populations

Enrolled Subjects – all subjects enrolled in the study

Evaluable Subjects – all subjects that are enrolled in the study and have received the study procedure.

All enrolled subjects will be accounted for. If a subject is enrolled in the study and does not undergo the study procedure, a description of the reason will be provided. Analysis of study endpoints will be performed on all evaluable subjects.

### 13.4 Primary Endpoint – Efficacy Analysis

The study hypothesis will be tested by calculating the change in NOSE scores from baseline to 26 weeks (baseline – 26 weeks). The lower limit of the one-sided 95% confidence interval will be calculated using the t-distribution. Should the lower limit exceed 15.0, then the null hypothesis will be rejected in favor of the alternative.

### 13.5 Secondary Endpoint – NOSE Responder Rate

The secondary efficacy endpoint is the percent of subjects that are considered a responder, where responder is defined as achieving a 15 point or greater improvement in the NOSE score from baseline to 26 weeks. Success for this endpoint is defined as a responder rate of 55% or greater.

### 13.6 Secondary Endpoint – Safety Analysis

Safety will be assessed by characterizing the type and frequency of adverse events reported at or following the study procedure, throughout the follow-up period. The number of events as well as the percent of subjects experiencing each event type will be calculated.

### 13.7 Adverse Events

All adverse events for subjects in the safety population will be reported.

- Serious Adverse Events
- Non-serious Adverse Events
- Device Related Adverse Event
- Device Related Serious Adverse Events

The following time intervals, based on the date of the procedure, will be considered:

- 0 days to 4 weeks
- 4 weeks to 12 weeks

- 12 weeks to 26 weeks

Results will include the number of subjects experiencing each type of event as well as the number of events.

## 13.8 Statistical and Analytical Methods

### 13.8.1 Demographics

Subject demographics will be summarized using descriptive statistics (mean, median, SD, minimum, maximum) and number of subjects for continuous variables (e.g., age), and frequency distributions (number and percentage of subjects) for categorical variables (e.g., gender, race).

### 13.8.2 Handling Dropouts, Loss-to-Follow-up or Missing Data

All efforts will be made to collect all data points in this study. The study hypothesis will be tested using all available data for the subjects in the efficacy patient population. If the primary endpoint is not available for all such subjects, then additional analyses will be performed in order to assess the potential effect of missing data on the study conclusions. First an analysis will be performed, treating all missing data points for the primary endpoint as 0 improvement. If the study conclusion is upheld using this type of worst-case scenario, no other analyses will be performed. Otherwise, a multiple imputation approach will be used. The propensity method will be used including the baseline, 4 week and 12 week NOSE scores if they are available. Fifteen imputed datasets will be generated and the study hypothesis will be repeated on the imputed dataset to determine if the study hypothesis is upheld.

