## 1.0 PROTOCOL SYNOPSIS

Study Title:	Prospective, Multi-Center, Non-Randomized Study to Evaluate Treatment of Nasal Airway Obstruction Using the Aerin Medical Device
Investigational Device:	Aerin Medical Vivaer™ Stylus
Device Description:	The Vivaer Stylus is a disposable handheld device capable of delivering bipolar radiofrequency energy to tissue.
Proposed Indication:	The Vivaer Stylus is indicated for the treatment of nasal obstruction by the modification of submucosal tissue including cartilage in the internal nasal valve area.
Study Objective:	The primary objective of this study is to evaluate the safety and efficacy of the Vivaer System for treating the nasal valve area to improve symptoms in those diagnosed with nasal airway obstruction.
Study Design:	Prospective, multi-center, non-randomized, Non-Significant Risk (NSR) safety and efficacy study.
Subject Population:	Male and female subjects who present with symptoms associated with nasal airway obstruction and meet the protocol eligibility criteria.
Study Procedure:	Subjects will have both nasal valves treated in a single treatment session. Follow-up visits will be scheduled and calculated from the treatment date. No repeat ("touch-up") procedures will be permitted during the 6-month (26-week) follow-up period.
Study Endpoints:	
Primary Endpoint – Efficacy: Improvement in subject-reported Nasal Obstruction Symptom Evaluation (NOSE) Score from Baseline to 26 weeks post study procedure. The primary efficacy endpoint will utilize the mean change in NOSE score from Baseline to 26 weeks post study procedure. The mean improvement in this score must be statistically significantly greater than 15 points for study success.
 
Secondary Endpoint – NOSE Responder Rate: A responder is defined as a treated subject who experiences at least a 15-point improvement in NOSE score from Baseline to 26 weeks post treatment. Success for this endpoint is defined as a responder rate of 55% or greater.
 
Secondary Endpoint – Safety: Safety will be assessed by characterizing the type and frequency of adverse events reported at or following the study procedure, throughout the follow-up period.

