Eligible subjects must meet the inclusion and exclusion criteria described in Sections 7.3 and 7.4. Any questions regarding a potential subject's eligibility for enrollment must be discussed with the Sponsor prior to scheduling the subject for the investigational procedure.

An estimated 45 treated subjects who complete the 26-week follow-up will be necessary to fulfill the primary endpoint data analysis. To allow for up to 10% attrition over the course of the study, a total of 50 subjects will be enrolled.

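### The success test leaves out treated subjects without a week-26 NOSE score, and the plan does not say whether its missing-data analyses affect success; regression imputation should be the deciding analysis

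*Combined protocol and SAP*

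**What the plan says.** - Section 1.0 ties success to one result: "The mean improvement in this score must be statistically significantly greater than 15 points for study success".
- Section 13.4 gives the rule: "The lower limit of the one-sided 95% confidence interval will be calculated using the t-distribution". The null is rejected if that limit exceeds 15.0.
- Section 13.8.2 names the data for that test: "The study hypothesis will be tested using all available data for the subjects in the efficacy patient population". The efficacy population it refers to is not among those defined in Section 13.3.
- Section 7.2 counts completers: "An estimated 45 treated subjects who complete the 26-week follow-up will be necessary to fulfill the primary endpoint data analysis".
- Section 13.3 says: "Analysis of study endpoints will be performed on all evaluable subjects". Evaluable means enrolled and treated.
- Section 1.0 lists as an additional evaluation: "Subject-reported NOSE score at 4-week and 12-week follow-up visits".
- If week-26 values are missing, Section 13.8.2 says that "additional analyses will be performed in order to assess the potential effect of missing data on the study conclusions". Missing values are first set to zero improvement. "If the study conclusion is upheld using this type of worst-case scenario, no other analyses will be performed". Otherwise multiple imputation follows, by the propensity method on baseline, week-4 and week-12 NOSE with fifteen datasets, to see whether the hypothesis is upheld.

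**The concern.** A treated subject with no week-26 score contributes nothing to the test that decides success, even when that subject's week-4 and week-12 scores are in the database. The trial has a single arm and a fixed 15-point bar, so no control arm offsets selective loss. If poor responders leave more often, the completer mean overstates the improvement; if good responders leave, it understates it.

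The plan does have safeguards. But they are described as assessing the effect of missing data, and no section makes success conditional on them or states a conclusion if both fail. Passing the zero-improvement analysis also ends the inquiry, although a subject can worsen, so zero is not a lower bound.

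**Working it through.** **1. The plan's own figure.** Inputs from Sections 13.1 and 13.2: mean 28.5, SD 30.3, bar 15, one-sided alpha 0.05. The standard error with 45 subjects is 30.3/√45 = 4.517, and the noncentrality is 13.5/4.517 = 2.99. Power from the noncentral t is 90.3% at N=45 and 89.7% at N=44, so 45 is correct, and 45/0.9 = 50. The sample size is not in dispute.

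**2. Where the analyses part company (5 of 50 missing, SD 30.3).**
- The primary test passes when the completer mean exceeds 15 + 1.680 × 4.517 = 22.59.
- With five zeros and completer mean m, the overall mean is 0.9m and the variance is (44 × 30.3² + 4.5m²)/49. The zero-improvement analysis passes when m exceeds 24.48.
- At m = 28.5 the zero-improvement lower limit is 18.54, a clear pass.
- Above 24.48 the plan stops. If all five missing subjects had the same change, success would be overturned below -3.8 (m = 25), -10.9 (m = 26) or -27.4 (m = 28.5).

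**3. False success without a dropout model.** Fix the true mean of all treated subjects at 15 and let the missing tenth average d. The completer mean is then (15 - 0.1d)/0.9. With n = 45 and the noncentral t, the available-case test succeeds in 6.4%, 8.0%, 10.0% and 12.3% of trials for d = 10, 5, 0 and -5.

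**4. False success with a dropout model.** Assumptions, none given in the documents except the SD and the 10%: 50 treated, 10% missing on average, true mean 15, SD 30.3, improvement multivariate normal across visits with correlation 0.6-0.8, and logistic loss. Moderate means log-odds 0.5 to 0.75 per SD, that is, odds multiplied by about 1.6 to 2.1. The written sequence is primary pass, then zero improvement, then propensity imputation if that fails; five propensity groups were assumed. There were 40,000 trials per setting (30,000 for the sequence), so simulation error is about 0.1 point at 5%.

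| Loss pattern | Available-case | Written sequence, if binding | Regression imputation |
|---|---|---|---|
| Random | 4.8-5.2% | 3.8% | 4.6-5.1% |
| Good responders leave (0.75, week 12) | 2.2-2.6% | not run | 4.6-5.1% |
| Poor responders leave (0.5, week 12) | 7.4-8.3% | 5.0-5.3% | 4.6-5.1% |
| Poor responders leave (0.75, week 12) | 8.7-10.2% | 6.2-6.3% | 4.6-5.1% |
| Poor responders leave (0.5, unseen week 26, correlation 0.7) | 9.2% | 6.5% | 6.6% |
| Poor responders leave (0.75, unseen week 26, correlation 0.7) | 12.3% | 8.4% | 7.6% |

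Under moderate week-12 loss the available-case bias is +0.9 to +1.7 points. At correlation 0.3 false success is about 6%. On a bounded scale (0-100 in steps of 5, assumed) the available-case test gives 4.3% under random loss and 7.0-8.2% under moderate loss, and imputation gives 4.2-4.8%. If lost subjects also lack a week-12 score, regression imputation gives 5.2-5.9% (week-12 dependence) or 6.6-8.1% (week-26 dependence).

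**5. How often the plan states no conclusion.** At mean 28.5 with random loss, the available-case test passes in about 90% of trials and zero improvement in about 80%, so they disagree in about 10%. Section 13.8.2 sends those trials to imputation. In 8,000 simulated trials imputation also failed in 1.2%; with moderate loss of poor responders (0.75, week 12) the figure was 3.0%.

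**The case against.** The strongest reply is that the plan's structure is coherent: an available-data primary test, backed by prespecified sensitivity analyses that start whenever any primary value is missing. Section 13.8.2 asks twice whether the result is *upheld*, which can be read as a condition on success. On that reading, regression imputation gains about one point under moderate loss and almost nothing when loss depends on the unseen week-26 score. This stands, and it limits the size of the point. It does not close it, because the text never says which result prevails.

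The dropout direction, its strength and the correlations are assumptions, and loss of good responders makes the available-case test conservative. That also stands.

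The zero-improvement analysis is a demanding check unless the lost subjects average about zero or worse. At the planning mean, overturning success needs an average worsening of 27.4 points. A tipping-point analysis therefore matters mainly near the threshold.

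A reader might infer that Sections 13.3 and 13.8.2 contradict each other. They need not: one says who belongs to the analysis, the other how absent values are handled. What is missing is a rule that lets a treated subject without a week-26 score count in the deciding test.

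**Conclusion.** The point holds in a limited form that depends on how the safeguards are read.

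- **If the safeguards are not binding**, which is a reading of the plan's silence, moderate loss of poor responders tied to week 12 raises false success from 5% to about 7-10%.
- **If they are binding**, the figure is 5-6%, and about 4% under random loss.
- **Regression imputation as the deciding analysis** gives about 5% in both situations. If loss depends on the unseen week-26 score it gives about 6.5-8%, close to the binding sequence and below the available-case 9-12%.

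All of this assumes 10% missing, a true mean of exactly 15 and the correlations stated above.

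Two stronger readings are tempting. A reader might infer that the plan is silent in about one trial in ten, because the primary and zero-improvement analyses disagree that often at planning values. It is not: imputation is prescribed next, and the case without a stated consequence is about 1% (about 3% with moderate loss of poor responders). A reader might also infer that the plan as a whole runs at 7-10% error. That range describes the available-case test alone, under one direction of loss.

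**What to change.** In Section 13.8.2, make the deciding analysis, on all evaluable subjects of Section 13.3, a multiple imputation by regression on baseline, week-4 and week-12 NOSE, combined by Rubin's rules. A mixed model for repeated measures would also serve. It replaces both the available-case test and the propensity step.

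Always report as supportive, not only after a failure:
- the available-case analysis;
- the zero-improvement analysis, labelled no improvement rather than worst case;
- a tipping-point analysis that extends below zero.

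State that the deciding analysis alone determines success, and how any disagreement will be described.

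The cost is SAP wording and a little programming; no new data are needed. At mean 28.5 and correlation 0.7, power under random loss is not reduced (91.4% against 90.4% for the available-case test). Under moderate loss of poor responders it is about 91% against an inflated 95%. Making zero improvement binding on its own is a poorer choice, because power under random loss falls to about 80%.
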